DSMB	Data and Safety Monitoring Board
FFR	Federal Financial Report
FWA	Federalwide Assurance
GAE	Genicular Artery Embolization
GCP	Good Clinical Practice
HIPAA	Health Insurance Portability and Accountability Act
ICF	Informed Consent Form
ICH	International Conference on Harmonisation
IRB	Institutional Review Board
ISM	Independent Safety Monitor
KOOS	Knee Injury and Osteoarthritis Outcome Score
MRA	Magnetic Resonance Angiogram
MOP	Manual of Procedures
N	Number (typically refers to participants)
NIH	National Institutes of Health
OA	Osteoarthritis
OHRP	Office for Human Research Protections
OHSR	Office of Human Subjects Research
PI	Principal Investigator
QA	Quality Assurance
QC	Quality Control
QOL	Quality of Life
SAE	Serious Adverse Event/Serious Adverse Experience
SOP	Standard Operating Procedure
TKA	Total Knee Arthroplasty
US	United States
VAS	Visual Analogue Scale

Protocol Summary

Title	Prospective pilot study on geniculate artery embolization for treatment of persistent knee pain post total knee arthroplasty
Short Title	Geniculate artery embolization for post TKA pain
Brief Summary	Single-arm, single-center, no sham or placebo, prospective pilot trial designed to evaluate the safety and efficacy of transcatheter arterial embolization in patients with persistent knee pain resistant to conservative management for at least 9 months after total knee arthroplasty (TKA). Eligible participants will receive geniculate artery embolization (GAE) using Embozene™ Color-Advanced Microspheres. Patients will be followed up for a total of 24 months after GAE.
Phase	Pilot study
Objectives	
Primary objective: to determine the effectiveness of GAE in reducing knee pain at 6-months post GAE in patients with persistent knee pain after TKA. This will be assessed by evaluating the clinical success rate defined as at least 15% improvement in Knee injury and Osteoarthritis Outcome Score (KOOS) pain score from baseline to follow-up visit at 6 months post-intervention without an increase in baseline incidence of pain medication use or intra-articular injections.
 
Secondary objectives:
 
 - To evaluate the safety of GAE - To determine feasibility and technical success of GAE - To determine whether GAE improves knee symptoms and quality of life (QOL) - To determine the effect of GAE on disease-specific biomarkers in the blood, urine, and synovial fluid of the target knee

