2.1 Primary Objective

The primary objective of the study is to determine the effectiveness of GAE in reducing knee pain at 6-month post intervention. This will be assessed by evaluating the clinical success rate defined as at least 15% improvement of KOOS pain score from baseline to follow-up visit at 6 months post GAE without an increase in baseline incidence of analgesics [59].

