3.1 Description of Study Design

This study is a single-center, single arm, no sham or placebo, open label, prospective pilot study designed to evaluate the safety and feasibility of GAE for the treatment of knee OA resistant to conservative management for at least 9 months post TKA. Enrolled patients will receive angiography and embolization of the one or more geniculate arteries in the affected knee using 100 μ m Embozene microspheres. If both knees are affected and fit eligibility criteria, the knee with the higher pain score on electronic VAS will be targeted.

The primary objective is to evaluate the effectiveness of GAE in reducing knee pain at 6 months. The primary objective will be evaluated by the clinical success rate. Clinical success is defined as at least 15% improvement in KOOS pain score at 6-month post GAE without increase in baseline use of analgesics. 40 patients will be required for this study to evaluate the primary outcome (complete 6-month visit). The study would accrue 50 patients to account for an attrition rate of 20%.

Change in KOOS pain score and VAS pain will be used as a measure of efficacy (i.e., pain reduction). KOOS questionnaire is a widely used, disease-specific measure. It was developed as an extension of the WOMAC score with the purpose of evaluating short-term and long-term symptoms and function in subjects with knee injury and osteoarthritis [60]. Specifically, the KOOS questionnaire assesses 5 domains: knee pain, knee symptoms/stiffness, knee function (activities of daily living), knee function (sports/recreational activities), and knee related quality of life.

The electronic VAS is a horizontal line with no markings on the scale except "No pain" on the left (score: 0 mm) and "worst possible pain" on the right end of the scale (score: 100 mm). Subjects mark the VAS to indicate their current pain level, with 0 mm representing "No pain" and 100 mm representing "worst possible pain". In our study, subjects will be asked to mark their pain level on a paper VAS on study questionnaire form and will give a score between 0 to 100, which will be documented on the appropriate eCRF.

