4.1 Inclusion Criteria

In order to be eligible to participate in this study, an individual must meet all the following criteria:

1. 30-85 years of age, of any gender
2. Knee pain resistant to conservative treatment for at least 9 months* post TKA performed for knee OA
3. Moderate to severe knee pain: pain VAS ≥ 40 mm
4. Willing, able, and mentally competent to provide informed consent and complete study questionnaires in English. The validated KOOS study questionnaires are only available in English.

* Conservative management is defined for the purpose of this study as use of analgesics (anti- inflammatory drugs, acetaminophen), or physical therapy and muscle strengthening exercises); 9-month duration of pain was selected because this time interval is adequate for knee pain to be considered refractory to conservative care.

Note: If both knees meet criteria, the one with a higher VAS score will be selected for the study (i.e., target knee).

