6.1 Study Procedures/Evaluations

6.1.1 Study Specific Procedures

- Imaging assessment with knee MRA (visits 2, 6, and 8):
 - Baseline and follow-up (at 6 and 24 months) knee MRA will be performed.
- Biological specimen collection (visits 2, 5, 6, 7, and 8):
 - Baseline and follow-up biomarker analysis from blood, urine, and knee aspirate (synovial fluid) will be obtained from participants.
- Administration of questionnaires or other instruments for patient-reported outcomes (visits 2, 5, 6, 7, and 8):
 - VAS questionnaire
 - KOOS questionnaire
 - Self-reported quality of life EQ-5D-5L questionnaire
 - Anchor pain questionnaire
- GAE procedure (visit 3)
- Medical history (visits 2, 5, 6, 7, and 8):
 - Complete medical history will be obtained from medical records if available and/or by interview during clinic visits.
- History of previous and concomitant treatment (visits 2, 5, 6, 7, and 8):
 - Knee injections and frequency
 - Medication history. Will focus on medications currently taken for the treatment of knee pain; including prescription and over-the-counter medications for pain.
 - Physical therapy and frequency
 - Weight loss / gain
- Focused physical examination (visits 2, 5, 6, 7, and 8):
 - Vital signs (temperature, blood pressure, heart rate, oxygen saturation, height, weight, BMI)
 - Focused knee examination.

Note: A discussion of the results of any study specific procedures (e.g., radiographic or other imaging or laboratory evaluations) will be provided to participant after the completion of the study unless this information represents a significant health-related issue.

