6.6 Prohibited Medications, Treatments, and Procedures

Not applicable.

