9.4.3 Analysis of the Secondary Endpoint(s)

Analysis of secondary endpoints include: (1) changes in the mean KOOS and VAS pain scores, the mean (2) the technical success rate (defined as the proportion of patients for whom the procedure was successfully completed); (3) the adverse event rate (defined as the proportion of patients showing each type of adverse event or any adverse event); (4) reduction in the usage of pain medication and the need for physical therapy. A point estimate and 95% confidence interval will be provided for each secondary outcome at each time and for the change in each outcome from baseline to each post-treatment follow-up visit. Changes in the outcomes from baseline to follow-up will be tested using the paired-sample Wilcoxon signed rank test for the KOOS and VAS scores and the McNemar test for the other measures which will be assessed as binary outcomes (e.g., whether or not the patient reported usage of pain medication on a daily basis).

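### The success definition guards against extra analgesics but not against a new non-drug treatment of the target knee before month 6, and no analysis rule says how such a patient is scored

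*Combined protocol and SAP*

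**What the plan says.** The success definition appears three times.

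- **Section 3.1:** "Clinical success is defined as at least 15% improvement in KOOS pain score at 6-month post GAE without increase in baseline use of analgesics".
- **Section 2.1:** the same 15% threshold, "without an increase in baseline incidence of analgesics".
- **Protocol Summary, Objectives:** the same threshold, "without an increase in baseline incidence of pain medication use or intra-articular injections".

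Other sections bear on treatment given after the embolization.

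- **Section 4.1** defines conservative management as analgesics "or physical therapy and muscle strengthening exercises".
- **Section 6.6**, headed "Prohibited Medications, Treatments, and Procedures", is marked as not applicable. Section 6.8 (rescue) deals only with limb ischemia.
- **Sections 6.1.1 and 6.4** record other treatment. Section 6.1.1 lists "Physical therapy and frequency" at baseline and at every follow-up visit from month 3. Section 6.4 records concomitant treatments and procedures.
- **Section 9.4.3** uses some of this in a secondary analysis of "reduction in the usage of pain medication and the need for physical therapy".
- **Section 4.7.1** lets the investigator withdraw a patient who newly meets an exclusion criterion. Sections 4.6 and 4.7.2 allow withdrawn patients to be replaced and do not count them toward the sample size.
- **Section 9.1** says that no formal SAP will be written.

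**The concern.** The clause on analgesics is there so that improvement bought with more medication is not credited to GAE. The same reasoning applies to other treatment of the target knee in the same six months, but the clause stops at drugs (and at injections, in the Summary only). With no control arm, any effect of such treatment goes into the GAE success rate.

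Entry requires a pain VAS of at least 40 mm and at least nine months of pain resistant to conservative treatment. It is plausible that some patients will seek further treatment within six months. The primary success rate, and the decision based on it, could then include successes that are not due to the embolization. Because no SAP is planned, no later document is due to settle the scoring before results are seen.

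**Working it through.** **Step 1. What happens to a co-treated patient under the text?** Take a patient who has a nerve ablation or knee surgery at month 2, improves by at least 15% on KOOS pain at month 6, and has not increased analgesics.

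- Sections 2.1 and 3.1: both conditions are met, so this is a success.
- Protocol Summary: no increase in injections either, so again a success.
- Section 6.6: the treatment breaks no prohibition.
- Section 4.2: the surgery exclusion is tied to screening, not to follow-up.
- Section 9.3: the analysis includes everyone treated who has reached the 3-month visit. It neither removes nor reclassifies anyone because of other treatment.
- Sections 9.2 to 9.4: no rule.

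The other route is withdrawal under section 4.7.1, which is discretionary. The patient may then be replaced (4.6, 4.7.2) and need not count among the 40. Neither route scores the patient as a non-success.

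**Step 2. The plan's own figure.** Section 9.5 gives 80.4% power at a realized level of 0.047 for 40 evaluable patients, testing 0.50 against 0.75. The exact binomial calculation does not give these values at n = 40:

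- n = 40, cut-off 26: P(X ≥ 26 | 0.50) = 0.0403 and P(X ≥ 26 | 0.75) = 0.946.
- n = 23, cut-off 16: P(X ≥ 16 | 0.50) = 0.0466 and P(X ≥ 16 | 0.75) = 0.804.

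The stated figures fit n = 23. That is a separate matter and the present point does not depend on it. The calculations below use n = 40.

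**Step 3. Which cut-off?** Section 9.2 has a one-sided hypothesis but reports a two-sided exact 95% interval, so two cut-offs are reasonable for rejecting 50%.

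- One-sided 5% test: 26/40 (65%), tail probability 0.0403.
- Two-sided 95% interval excluding 50%: at 26/40 the Clopper-Pearson interval is 48.3% to 79.4%, which includes 50%. At 27/40 it is 50.9% to 81.4%. The cut-off is therefore 27/40, tail probability 0.0192.

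**Step 4. Effect of co-treatment successes.** Let the GAE-attributable success rate be 0.50. Let c be the share of all patients who count as successes only because of another treatment. The documents give no value for c, so it is assumed. The chance of rejecting 50% is P(X ≥ r | n = 40, p = 0.50 + c).

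| Extra successes per 40 | c | Cut-off 26/40 | Cut-off 27/40 |
|---|---|---|---|
| 0 | 0 | 4.0% | 1.9% |
| 1 | 2.5% | 7.6% | 4.0% |
| 2 | 5% | 13.3% | 7.5% |
| 4 | 10% | 31.7% | 21.1% |

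**Step 5. Sensitivity at the boundary.** Rescoring one patient moves 26/40 (one-sided p = 0.040) to 25/40 (p = 0.077). Rescoring two gives 24/40 (p = 0.134).

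**Step 6. Cost of the stricter rule.** Suppose the planned 75% had included co-treatment successes. With the 26/40 cut-off, power falls from 94.6% to 89.0% if c = 2.5% (p = 0.725), and to 80.7% if c = 5% (p = 0.70).

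**The case against.** Counting outcomes whatever else the patient received is a defensible strategy for a single-arm pilot, provided that it is stated. This stands as a principle, but the plan does not state it, and its analgesic clause points the other way.

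A reader might infer several stronger claims. The documents do not support them.

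- **That the bias always favours GAE.** The existing clause already fails a co-treated patient who needs more analgesics or has not improved by 15% at month 6. Inflation requires a patient who would otherwise have failed, who then gains at least 15%, and whose analgesics do not increase.
- **That repeat embolization is equally open.** Sections 5.1.7 and 5.2.1 plan one session, so a repeat would depart from the protocol. It is not a good example.
- **That revision surgery is always scored as a success.** Known TKA complications are excluded at entry, and a new one may lead to withdrawal under section 4.7.1. But withdrawal is discretionary and does not make the patient a failure.
- **That nothing else guards against physical therapy.** Pain must have resisted conservative care, and section 9.4.3 analyses the need for physical therapy over time. The protection is partial: the definition joins analgesics and physical therapy by an or, so a patient need not have tried the latter, and the secondary analysis is not linked to individual success.

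The numbers are also open to challenge. Ten points at a true 50% means that one in five non-responders is converted by other treatment alone, which is the high end of the illustration. A drug nerve block might be read as an analgesic. The point is clearest for nerve ablation, knee surgery and new physical therapy.

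**Conclusion.** The gap is real and should be closed. All three definitions leave out new non-drug treatment of the target knee, nothing is prohibited, and no analysis rule covers it. As written, a co-treated patient who improves with stable analgesics is a GAE success, or may be withdrawn and replaced.

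The documents do not show that the success rate will be inflated, or by how much. The table in the working is conditional on an assumed co-treatment share, a true rate of 50%, 40 evaluable patients, and the choice between 26/40 and 27/40. It concerns rejection of 50%. Section 9.2 also ties a declaration of success to a 75% response rate, which these figures do not address. What they show is that one or two patients are enough to matter near the cut-off.

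**What to change.** 1. Use one success definition in the Protocol Summary and sections 2.1 and 3.1, which also settles whether injections are included. In it, score as non-success any patient who has a new interventional or surgical treatment of the target knee between Day 0 and the 6-month visit.
2. State in sections 4.6, 4.7.2 and 9.3 that such patients stay in the denominator and are not replaced, even if they are withdrawn.
3. Add to section 9.4.2 a pre-specified sensitivity analysis that also scores new or increased physical therapy of the target knee as non-success.
4. Settle these rules before the preliminary analysis of 10 patients.

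Do not add 12- or 24-month analyses that leave out co-treated patients. Those would condition on an event after treatment and could drop likely failures.

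The change affects scoring only and does not limit what care any patient may receive. It uses data that sections 6.1.1 and 6.4 already collect. The cost is a few sentences, one extra analysis, and a slightly lower reported success rate if such treatments occur.

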3.2 Study Endpoints

3.2.1 Primary Study Endpoints

The primary endpoint is the KOOS pain score at 6 months post intervention.

3.2.2 Secondary Study Endpoints

Secondary efficacy endpoints are:

1. KOOS scores at 3-, 6-, 12-, and 24-month post GAE
2. VAS pain at 3-, 6-, 12-, and 24-month post GAE
3. Self-reported quality of life using EQ-5D-5L scale at 3-, 6-, 12-, and 24-month post GAE
4. MRA findings at 6- and 24-month post GAE
5. Pain medication usage at 3-, 6-, 12-, and 24-month post GAE
6. Feasibility / technical success
7. Knee-specific biomarkers at 3-, 6-, 12-, and 24-month post GAE
8. Number/rate, severity, and description of complications, adverse events, or poor outcomes that are secondary to the procedure, which will be summarized using counts and simple statistics (i.e., mean number of patients with complications.)

3.2.3 Exploratory Endpoints

Not applicable.

4 Study Enrollment and Withdrawal

4.1 Inclusion Criteria

In order to be eligible to participate in this study, an individual must meet all the following criteria:

1. 30-85 years of age, of any gender
2. Knee pain resistant to conservative treatment for at least 9 months* post TKA performed for knee OA
3. Moderate to severe knee pain: pain VAS ≥ 40 mm
4. Willing, able, and mentally competent to provide informed consent and complete study questionnaires in English. The validated KOOS study questionnaires are only available in English.

* Conservative management is defined for the purpose of this study as use of analgesics (anti- inflammatory drugs, acetaminophen), or physical therapy and muscle strengthening exercises); 9-month duration of pain was selected because this time interval is adequate for knee pain to be considered refractory to conservative care.

Note: If both knees meet criteria, the one with a higher VAS score will be selected for the study (i.e., target knee).

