6.3 Study Schedule

6.3.1 Screening (visit 1; Day -30 to -2)

In rheumatology, orthopedic, or vascular and interventional radiology clinic

- Obtain informed consent of potential subject
- Provide a copy of informed consent and key information sheet to subject
- Review subject's eligibility based on eligibility criteria
- Schedule study visits for eligible participants

Note: if subject prefers, visits 1 and 2 can be combined and procedures of these visits may be performed on the same day after completion of screening and obtaining informed consent.

Those candidates who are disqualified from study entry will be logged into the Screening Log with a reason for no study entry. A copy of the consent will be provided to the subject and the original filed in the study files.

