6.3.3 Interventional visit (visit 3, Day 0)

- Performed within 30 days of visit 2
- Geniculate artery embolization (GAE) procedure
- Record any immediate complications / adverse events detected during the procedure or observation period (if applicable)
- Subjects will be given a phone number to reach a physician 24 hours a day to report any adverse symptoms and receive medical advice

6.3.4 Follow up Visits:**6.3.4.1 Follow up safety visit (Visit 4; day 7 ± 3 days)**

- Subjects will be seen in clinic (in-person or telemedicine) or contacted by phone per subject's preference on day 7(± 3 days). As most complications of the procedure will be evident within this period, this visit is to evaluate for early AE's. If AE is suspected based on change in pain scores, functionality, or other signs / symptoms, further assessment and management will be performed based on the nature and severity of suspected AE.

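### Only one pre-treatment VAS/KOOS assessment is scheduled, and the protocol does not say which VAS reading qualifies the patient or picks the knee; as scheduled, regression to the mean counts as improvement in the secondary VAS change.

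*Combined protocol and SAP*

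**What the plan says.** Entry criterion 3 in Section 4.1 is "Moderate to severe knee pain: pain VAS ≥ 40 mm". It asks for no repeat or averaged score. The note to the same section adds: "If both knees meet criteria, the one with a higher VAS score will be selected for the study". Section 3.1 repeats the knee rule and describes the scale as momentary: "Subjects mark the VAS to indicate their current pain level".

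The assessment times are in Section 6.1.1: "Administration of questionnaires or other instruments for patient-reported outcomes (visits 2, 5, 6, 7, and 8"). Visit 2 is therefore the only one before treatment. Section 6.3.1 reviews eligibility at visit 1 but lists no questionnaire there, and it allows that "if subject prefers, visits 1 and 2 can be combined". Section 6.3.3 lists no questionnaire on the procedure day, which is to be "Performed within 30 days of visit 2". The Schedule of Events shows a single pre-treatment mark for VAS and for KOOS.

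Section 9.4.3 tests change from baseline within patients by the Wilcoxon signed rank test. The trial has one arm and no sham. The primary outcome is a gain of at least 15% in KOOS pain at 6 months without more analgesic use; KOOS has no entry threshold.

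**The concern.** A current-pain score is the patient's usual level plus a transient part. Patients admitted because the score reached 40 mm, and knees chosen because theirs was the higher score, have a transient part that is positive on average. If the same score is then the baseline, the return to the usual level appears as a fall in pain. A control arm would show the same fall and cancel it, and a second pre-treatment reading would remove it. The plan provides neither.

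What is directly at stake is the VAS change at each follow-up visit and its signed-rank test. KOOS pain, taken at the same sitting, can be affected only as far as its day-to-day error moves with that of the VAS.

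**Working it through.** The plan gives no figure for regression to the mean, so there is none to reproduce. It also gives no VAS SD or test-retest reliability for post-TKA patients. Those are assumptions below, shown as ranges.

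**1. Threshold effect on VAS, no treatment effect.** With a normal score of mean μ, SD σ and reliability r, entry at 40 mm and an independent second reading:

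spurious fall = (1 − r) · σ · φ(z) / [1 − Φ(z)], where z = (40 − μ)/σ.

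| μ | σ | r | z | φ(z) | 1 − Φ(z) | Fall (mm) |
|---|---|---|---|---|---|---|
| 45 | 20 | 0.6 | −0.25 | 0.387 | 0.599 | 0.4 × 20 × 0.646 = 5.2 |
| 50 | 20 | 0.6 | −0.50 | 0.352 | 0.692 | 0.4 × 20 × 0.509 = 4.1 |
| 60 | 20 | 0.6 | −1.00 | 0.242 | 0.841 | 0.4 × 20 × 0.288 = 2.3 |
| 60 | 20 | 0.8 | −1.00 | 0.242 | 0.841 | 0.2 × 20 × 0.288 = 1.2 |
| 76 | 14 | 0.6 | −2.57 | 0.0146 | 0.995 | 0.4 × 14 × 0.0147 = 0.08 |

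The last row uses the only VAS baseline of this kind in the documents, the 20-patient native-knee cohort in Section 1.2.2. Simulation agrees with the formula. When a later, independent pre-treatment reading is used as the baseline, the simulated fall is about 0 mm.

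**2. Knee choice.** If every patient had two qualifying knees and the higher score were taken, the simulated fall is 2.9 to 8.0 mm for means of 45 to 60 mm (SD 20, r 0.6 to 0.8). It is 0.8 to 4.0 mm for 76 ± 14 mm (r 0.5 to 0.9). These are upper bounds, because the share of such patients is not stated.

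**3. Consequence for the VAS test.** Over a wider grid (mean 50 to 60, SD 20 to 25, r 0.5 to 0.9, threshold only), the chance of a nominally significant VAS fall at n = 40 with no effect is about 6% to 47%, against 2.5% nominal in that direction. At the top of the range the fall is 7.0 mm and the SD of change 23.3 mm. Then 7.0/(23.3/√40) = 1.90, and Φ(1.90 − 1.96) ≈ 0.47 or 0.48. With 76 ± 14 mm the chance is about 3%, close to nominal.

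**4. Spill-over to the primary responder rate.** Assumed: KOOS pain mean 45, SD 15, and a 15% gain read as relative to baseline. Error correlation means the size of the same-day correlation between VAS and KOOS error. The analgesic condition is left out and could only lower the rates.

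| Setting | Error correlation | Same-day baseline | Separate baseline | Gap (points) |
|---|---|---|---|---|
| VAS mean 45, r 0.6 | 0.5 | 39% | 34% | about 5.4 |
| VAS mean 45, r 0.6 | 0.2 | 36% | 33% | 2.2 |
| VAS mean 45, r 0.6 | 0 | 34% | 34% | 0 |
| VAS mean 60, r 0.8 | 0.5 | 28% | 27% | 1.3 |

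The true-score correlation is 0.8 in size, except 0.6 in the second row.

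**5. Does the primary decision move?** In an exact one-sided 5% test of 0.50 with 40 patients, the smallest rejecting count is 26 (tail probability 0.0403). The 0.047 in Section 9.5 differs; that is a separate matter and this point does not depend on it. At an untreated rate of 39.2%, P(≥ 26 of 40) = 0.0009. The highest rate found on any assumptions tried was 46% (mean 50, SD 25, r 0.5, every patient with two qualifying knees), which gives 0.012. Both rates are below 50%.

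**The case against.** The strongest objection is that the documents never say one reading does all three jobs. Section 6.3.1 reviews eligibility at visit 1 and then schedules visits for eligible patients. Since criterion 3 is a VAS score, some VAS must be known by then. If that is an unscheduled visit 1 reading and visit 2 falls on another day, most of the threshold effect disappears. This stands. The triple role is an inference from the schedule, and the Schedule of Events cannot settle it because its columns are broken in the text available. But a visit 1 VAS is not in the plan either, and combining the visits removes any separation of days.

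A reader might infer that the primary result is inflated to the point of a false success. The documents do not support that. KOOS has no entry threshold, the spill-over rests wholly on an assumed error correlation, and the rate stays below the null. Most of the 27% to 39% is ordinary measurement noise that a separate baseline would not remove.

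A reader might also blame the gap of up to 30 days before treatment. The bias comes from reusing a selected reading; the length of the gap does not enter the calculation.

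Nine months of resistant pain limits the transient part, but does not remove it from a score of current pain. The cohort at 76 ± 14 mm suggests that the threshold may hardly matter. It is a native-knee cohort, so it does not settle the question for post-TKA patients.

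**Conclusion.** The point holds in a limited form. The plan schedules one pre-treatment VAS/KOOS assessment and does not assign readings to purposes. Followed as written, it biases the secondary VAS change toward improvement, with no control to correct it. The threshold contributes about 0 mm if enrolled patients sit far above 40 mm, and about 1 to 5 mm if the population mean is 45 to 60 mm with SD 20 and reliability 0.6 to 0.8. Knee choice adds to this only in patients with two qualifying knees.

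The effect on the primary responder rate is indirect: 0 to about 5 percentage points for an assumed same-day error correlation of 0 to 0.5. It uses up some of the margin below the 50% null, which the documents do not derive from untreated course, but does not close it. The change is worth making because the bias is avoidable at little cost, and a pre-treatment estimate of it cannot be recovered after embolization.

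**What to change.** - Add to Section 6.3.1 a VAS for each candidate knee at visit 1, and state that this reading decides criterion 3 and the target knee.
- Take the baseline VAS and KOOS on a different day, after eligibility and target knee are fixed. This can be visit 2 when it is separate, and otherwise Day 0 before sedation. Using Day 0 before sedation for all patients would keep the baseline setting uniform.
- State in Sections 6.3 and 9.4 and in the Schedule of Events that only this second set is the baseline for clinical success and for every change in 9.4.3.
- Report the change from qualifying to baseline VAS as a pre-treatment estimate of regression to the mean.

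The cost is one extra VAS and, where the baseline moves to Day 0, a questionnaire set on that day. There are three drawbacks: minor patient burden, possible influence of the procedure day on the scores, and a slightly less favourable estimate of change. Entry threshold, treatment and sample size are untouched. The change does not deal with placebo response or natural course, which a single-arm trial cannot separate from treatment effect.
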